4.2.2. Elimination from the Solicited Safety Set

Code 1030 (Study vaccine not administered at all for P-Fx and NP-Fx groups), code 800 (fraudulent data), code 900 (invalid informed consent) and code 1160 (no post-vaccination solicited safety data) will be used for identifying subjects eliminated from the solicited safety set.

4.2.3. Elimination from Per-protocol analysis Set for analysis of immunogenicity and efficacy (PPS) And from the Adaptive PPS for analysis of efficacy (APPS)

4.2.3.1. Excluded subjects

A subject will be excluded from the PPS and the APPS analysis under the following conditions

Code	Condition under which the code is used	Visit (timepoints) where the code is applicable	Applicable for analysis set
800	Fraudulent data	All	PPS, APPS
900	Invalid informed consent or fraudulent data	All	PPS, APPS
1030	Study vaccine not administered at all	All	PPS, APPS
1040	Administration of concomitant vaccine(s) forbidden in the protocol 
 • Any investigational or non-registered vaccine other than the study vaccines used during the study period. • A vaccine not foreseen by the study protocol administered during the period starting seven days before each dose and ending seven days after each dose of vaccines administration. 	All	PPS
1070	Vaccination not according to protocol 
 • Administration not according to protocol for reason specified by the investigator, other than side, site and route. 	All	PPS, APPS
1080	Good Manufacturing Practice No-Go: Vaccine temperature deviation	All	PPS
1090	Expired vaccine administered	All	PPS
2010	Protocol violation (inclusion/exclusion criteria) 
 • Eligibility criteria not met with an impact on immunogenicity or efficacy data 	All	PPS

Code	Condition under which the code is used	Visit (timepoints) where the code is applicable	Applicable for analysis set
2040	
Administration of any medication forbidden by the protocol
 
 Any investigational or non-registered product drug other than the study vaccines used during the study period. Immunosuppressants or other immune-modifying drugs administered chronically (i.e. more than 14 days in total) during the study period. For corticosteroids, this will mean prednisone ≥ 20 mg/day (for adult subjects), or equivalent. Inhaled and topical steroids are allowed. Long-acting immune-modifying drugs administered at any time during the study period (e.g. infliximab). A vaccine not foreseen by the study protocol administered during the period starting seven days before dose and ending seven days after the dose of vaccine administration. Immunoglobulins and/or any blood products administered during Drugs known to have anti-Plasmodium properties, used during the challenge period before identification of parasitemia 	All	PPS
2050	Underlying medical condition forbidden by the protocol which may influence the efficacy endpoints	All	PPS
2080	Subjects did not comply with challenge schedule (see Tables 1)	All	PPS
2090	Subjects did not comply with blood sample schedule (see Tables 1)	All	PPS
2100	Serological results not available for all visits for anti-CS	All	PPS
2120	Obvious incoherence or abnormality or error in immunogenicity (antibody) data	All	PPS
3000	Subject did not undergo challenge	All	PPS, APPS

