\*\*A blood sample for assessment of parasitemia (blood smear and PCR) will be collected daily for 14 days (from Day 27 [Visit 4] to Day 40 [Visit 17]) and then every two days for 9 days (Day 42 [Visit 18], Day 44 [Visit 19], Day 46 [Visit 20], Day 48 [Visit 21] and Day 50 [Visit 22]). Exceptionally this can occur within 1 or 3 days if the subject cannot make the visit or for schedule conflicts. For subjects who develop malaria (positive blood smear), blood smear and PCR may be discontinued once the subject has three consecutive negative smears (separated by more than 12 hours) following initial treatment.

a Including a check of NHANES-I criteria and electrocardiogram [see [APPENDIX C](#)].

b The screening laboratory results (HIV, HCV, HBsAg, ALT, AST, creatinine, hemoglobin, leukocytes [WBC], platelets, and urine β-HCG) must be checked during the screening activities and before vaccination.

c There is no specific section in the eCRF to record the contraindications. The absolute contraindications to administration of study vaccine or challenge have to be recorded in the AE or SAE section of the eCRF.

d Blood sampling for hematology and biochemistry analysis includes ALT, AST, creatinine, hemoglobin, leukocytes (WBC), and platelets.

e Blood sample might not be drawn at Visit 1 if this visit occurs less than one week after the screening visit, at the discretion of the investigator

f Return of diary cards for the collection of solicited AEs

g Return of diary cards for the collection of unsolicited AEs

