2. STUDY DESIGN

Figure 1 Study design overview

SCR = screening; **V** = visit; **D** = day; **BS** = blood sampling

*Screening visit applicable for the groups from the MALARIA-092 study receiving the fractional booster dose

**Screening visit applicable for subjects in the infectivity control group

***Blood sample for biochemistry and hematology parameters will be collected the day of first parasitemia and blood sample for assessment of parasitemia (blood smear and PCR) will be collected daily for 14 days (from Day 27 [Visit 4] to Day 40 [Visit 17]) and then every two days for nine days (Day 42 [Visit 18], Day 44 [Visit 19], Day 46 [Visit 20], Day 48 [Visit 21] and Day 50 [Visit 22]). Exceptionally this can occur within 1 or 3 days if the subject cannot make the visit or for schedule conflicts.

The following table gives the intervals between study visits at defined visits to apply, as described in the protocol:

Table 1 Intervals between study visits for the P-Fx and NP-Fx groups

Interval	Optimal length of interval*	Allowed interval**
Screening #1 → Visit 1	1 to 90 days	-
Visit 1 → Visit 2	7 days	6-8 days
Visit 1 → Visit 3 (challenge)	21 days	21-28 days
Visit 3 → Visit 22	28 days	21-35 days
Visit 22 → Visit 23	140 days	126-154 days

*Whenever possible the investigator should arrange study visits within this interval.

**Subjects may not be eligible for inclusion in the Per-Protocol Set (PPS) for analysis of immunogenicity and efficacy if they make the study visit outside this interval.

Table 2 Intervals between study visits for the infectivity control group

Interval	Optimal length of interval*	Allowed interval**
Screening #2 → Visit 3 (challenge)	1 to 90 days	-
Visit 3 → Visit 22	28 days	21-35 days

*Whenever possible the investigator should arrange study visits within this interval.

**Subjects may not be eligible for inclusion in the PPS for analysis of immunogenicity and efficacy if they make the study visit outside this interval.

The following group names will be used for the statistical analyses:

Group order in tables	Group label in tables	Group definition for footnote
1	P-Fx	Pooled subjects from the MALARIA-092 study vaccinated with RTS,S/AS01 (different doses/formulations) and protected following the first challenge who received a Fx booster dose of RTS,S/AS01E

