4.1.4. Per-protocol set for analysis of immunogenicity and efficacy

The Per-Protocol Set (PPS) for analysis of immunogenicity and efficacy will include all subjects included in the ITTS who fulfilled all eligibility criteria and received the Fx dose according to protocol procedures, did not use any medication, vaccine or blood products forbidden by the protocol, did not report any underlying medical condition influencing the efficacy response, had available data concerning immunogenicity endpoint measures, and underwent *P. falciparum* challenge. This will include subjects for whom assay results are available for antibodies against at least one study vaccine antigen after Day 1.

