5.3. Efficacy

5.3.1. Analysis of efficacy planned in the protocol

The analysis of efficacy will be performed on the PPS for analysis of immunogenicity and efficacy.

Efficacy will be assessed by comparison of *P. falciparum* parasitemia incidence and time-to-onset of *P. falciparum* parasitemia after sporozoite challenge. The analysis of the primary objective will be based on blood smears results; additional exploratory analyses will be performed based on PCR results (tertiary objectives).

Vaccine efficacy (VE) is defined as $100 * (1 - \text{Relative Risk})$. Relative risk of infection and 95% CI will be calculated.

Fisher's Exact test will be used for the comparison of *P. falciparum* parasitemia incidence after challenge between each one of the study groups (P-Fx and NP-Fx) and the infectivity control group.

Kaplan-Meier analysis will be performed on time-to-onset of *P. falciparum* parasitemia, for comparisons between each one of the study groups (P-Fx and NP-Fx) and the infectivity control group, using the log-rank statistic.

The same methodology will be applied for the evaluation of the study groups (P-Fx vs. NP-Fx) versus each other. If there are sufficient evaluable subjects (at least a 1:2 ratio between vaccinated and control groups) to draw some conclusions, descriptive analyses based on initial group assignment versus control will be performed.

All statistical tests will be two-tailed at 5% significance level.

Risk periods

For the analyses of time-to-onset of parasitemia (Kaplan-Meier and log-rank), time-at-risk will start on first day of challenge. Time-at-risk will be censored on Visit 22 (Day 50; 28 days post-challenge), drop-out date, start date of anti-malarial treatment or date meeting an endpoint, whichever occurs first. Time-at-risk will be calculated as: censor date – challenge date + 1.

For the analysis of proportion affected (relative risk), all subjects included in the PPS for analysis of immunogenicity and efficacy will be considered at risk of infection and no censoring or elimination will be applied for subjects not completing the entire protocol defined post-challenge follow-up (Day 50; 28 days post challenge).

Case definition

The following will be used as case definition of *P. falciparum* infection:

Asexual blood stage *P. falciparum* parasite density > 0 detected by blood slide reading (or PCR for tertiary objectives).

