7.2. Statistical considerations for interim analyses

A descriptive analysis to evaluate vaccine efficacy against infection of *P. falciparum* will be performed on the Adapted PPS for analysis of efficacy at the time of the interim analysis and will not be part of the CSR. Note that the main objective of the study linked to this endpoint will be analysed at the end of the study, on the PPS for analysis of immunogenicity and efficacy and can output different results. At the same time, we will perform some immunogenicity and safety/reactogenicity analyses, on data as clean as possible. All the analyses will be re-done during the final analysis which will be presented in the CSR.

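### A late or missed Day 190 blood sample can remove a vaccinee with a known Day 50 outcome from the final primary efficacy analysis, a route that does not exist for controls

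*SAP*

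**What the plan says.** **Set and timing.** SAP 5.3.1, following Protocol 11.9, states: "The analysis of efficacy will be performed on the PPS for analysis of immunogenicity and efficacy". SAP 7.2 adds that the main objective "will be analysed at the end of the study, on the PPS for analysis of immunogenicity and efficacy and can output different results". The interim efficacy analysis uses the APPS.

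**End of the outcome.** Under SAP 5.3.1 (risk periods), time at risk closes at Visit 22, Day 50, 28 days after challenge.

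**Serology-based exclusions.** In SAP 4.2.3.1, three codes apply to the PPS but not to the APPS, each at all timepoints:
- code 2090, "Subjects did not comply with blood sample schedule (see Tables 1");
- code 2100, "Serological results not available for all visits for anti-CS";
- code 2120, for incoherent or erroneous antibody data.

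**Window.** SAP Table 1 allows 126 to 154 days from Visit 22 to Visit 23. Its footnote says subjects may lose eligibility for the set "for analysis of immunogenicity and efficacy if they make the study visit outside this interval".

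**Set definition.** SAP 4.1.4 includes subjects for whom "assay results are available for antibodies against at least one study vaccine antigen after Day 1".

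**Optional sample.** Protocol Table 4, footnote e: "Blood sample might not be drawn at Visit 1 if this visit occurs less than one week after the screening visit".

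**The concern.** A blood slide decides the primary endpoint; an antibody result plays no part in it. If membership of the efficacy set depends on a blood draw made about 140 days after slide follow-up closed, the analysis conditions on something that happened after the outcome. Because only vaccinees have that later draw, the exclusion acts on one side of each comparison. With about 20 subjects per group, a few exclusions can move the VE estimate noticeably in either direction with no change in any slide reading. SAP section 6 calls all analyses descriptive, so the estimate is the main product of the trial, and it is the estimate that is exposed.

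**Working it through.** **1. Passages side by side**

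| Step | Source | Content |
|---|---|---|
| Outcome complete | SAP 5.3.1 | Visit 22, Day 50 |
| Final efficacy set | SAP 5.3.1 and 7.2 | PPS |
| Exclusion rule | SAP 4.2.3.1, code 2090 | Blood sample schedule, all timepoints, refers to Table 1 |
| Last row of Table 1 | SAP section 2 | Visit 22 to Visit 23, 126–154 days |
| Blood samples at Visit 23 | Protocol Table 4 | Antibody and PBMC/plasma only; no slide or PCR |
| Control schedule | Protocol Table 5 | Ends at Visit 22; no antibody sample at any visit |

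The chain is complete without code 2100. SAP 5.3.1 rules out elimination for incomplete post-challenge follow-up, but only for subjects already in the PPS, so it does not protect someone whom code 2090 has removed.

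**2. Code 2100.** It can mean that any scheduled anti-CS result is missing (strict), or that no result exists at any visit (loose). The strict reading removes vaccinees whose Day 1 sample was omitted as the protocol permits, and it contradicts the requirement of one antigen result after Day 1. It also removes every control. The loose reading and the serology clause of SAP 4.1.4 do not spare controls either if applied literally, since controls have no antibody results.

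**3. The plan's own power figure.** Protocol 11.4 takes 20 per arm, 19/20 controls and 6/20 vaccinees infected, and a Fisher exact test. Exact enumeration over two binomials, two-sided, gives for VE of about 68/58/47%:
- alpha 0.05: 99.7 / 97.4 / 89.4%;
- alpha 0.025: 99.1 / 94.6 / 81.8%, which are the tabulated values.

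The stated 99% holds. The table matches 0.025 although the text gives p < 0.05; that does not affect this point.

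**4. Effect on VE.** Formula: VE = 1 − (infected/n)/0.95, where 0.95 = 19/20. The number removed is an assumption: 2 to 4 of 20 (10–20%).

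| Removed | Infected/n | Calculation | VE |
|---|---|---|---|
| None | 6/20 | 1 − 0.300/0.95 | 68.4% |
| 2 uninfected | 6/18 | 1 − 0.333/0.95 | 64.9% |
| 2 infected | 4/18 | 1 − 0.222/0.95 | 76.6% |
| 4 uninfected | 6/16 | 1 − 0.375/0.95 | 60.5% |
| 4 infected | 2/16 | 1 − 0.125/0.95 | 86.8% |

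Starting from 10/20 infected (VE 47.4%), removing 4 gives 34.2% (10/16) to 60.5% (6/16).

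**5. How extreme the bounds are.** If removal of 4 from 6 infected and 14 uninfected were unrelated to outcome, the chance that all four were infected is C(6,4)/C(20,4) = 15/4845 = 0.3%. The chance that all four were uninfected is C(14,4)/C(20,4) = 1001/4845 = 20.7%.

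**6. Effect on power.** With 16 vaccinees and 20 controls, power at VE 68/58/47% is 99.5 / 96.8 / 88.0% at alpha 0.05, and 98.5 / 92.4 / 77.6% at 0.025. The loss is 0.2 to 1.4 points at 0.05 and 0.6 to 4.2 points at 0.025.

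**The case against.** Much can be said for the plan. All analyses are labelled descriptive. The interim result, which feeds the field-trial decision, already uses the APPS without these codes. The SAP openly says the two results may differ, and PPS exclusions will be tabulated. The Table 1 footnote is permissive. At the four-removed bounds from 6/20, Fisher p-values remain 0.0003 (6/16) and 0.0000004 (2/16). These arguments reduce the consequence but leave the mechanism in place: SAP 4.2.3.1 states exclusion as a rule, and any discretion would be used after outcomes are known in an open-label trial. SAP 7.2 keeps the interim APPS efficacy analysis out of the study report. Its remark that analyses will be repeated at the end might cover the APPS, but does not say so.

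A reader might infer more than the documents support:
- *Anti-CS results are required at every visit to Day 190.* Code 2100 does not establish this, because it has two readings.
- *A missed Day 50 antibody sample is also post-outcome information.* It is drawn at Visit 22, with the last slide, so it is not cleanly separate from slide follow-up.
- *All visit-window exclusions fall on vaccinees.* SAP Table 2 carries the same footnote for controls from Visit 3 to Visit 22.
- *The protocol's 20% drop-out predicts the loss.* It is already used to reach the group size: 100 × 0.8 × 0.8 × 0.32 = 20.5. It is also not a rate of missed Day 190 samples.
- *Interim and final results would differ only for reasons unrelated to efficacy.* The two sets also differ by codes 1040, 1080, 1090, 2010, 2040, 2050 and 2080, several of which bear on efficacy.

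**Conclusion.** The point holds for the Day 190 route. As written, code 2090 with Table 1 lets a blood draw after the outcome decide whether a vaccinee counts in the final primary efficacy analysis, with no equivalent for controls. Code 2100 is a separate ambiguity that must be reconciled with SAP 4.1.4.

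The issue is possible selection bias, not power. Its size cannot be predicted: the documents give no rate of late or missed samples and no evidence that Day 190 attendance depends on slide status. Under an assumed loss of 2 to 4 of 20, the bounds around 68.4% are 64.9–76.6% and 60.5–86.8%. They show how far the estimate could move; they are not an expected bias.

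**What to change.** 1. For VE, Fisher and Kaplan-Meier/log-rank, do not apply codes 2090, 2100 and 2120 or the serology requirement of the PPS. Use them only to drop the affected timepoints from immunogenicity analyses.
2. Keep the efficacy-relevant codes in the final efficacy set, including 2010, 2040, 2050 and 2080. Simply making the current APPS primary would not do this: it omits code 2040, which covers anti-*Plasmodium* drugs taken before parasitemia is identified, and code 2080 on the challenge schedule. Because the proportion analysis eliminates no one for incomplete follow-up, a slide-negative subject on such drugs would count as uninfected.
3. State that challenged controls belong to the efficacy sets. Both set definitions mention receipt of the Fx dose, which controls never receive.
4. Reword code 2100 to one meaning, consistent with SAP 4.1.4 and the optional Day 1 sample.
5. Report the APPS efficacy result beside the final one in the study report so that interim and final can be compared. Reconcile code 2010, listed for the PPS only, with the APPS definition, which requires all eligibility criteria.

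The cost is a wording change to SAP sections 4 and 5.3.1 and SAP 7.2, with matching text in Protocol 11.5, 11.9 and 11.13.2. The downside is that efficacy and immunogenicity tables may have slightly different denominators. No new data are needed.

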5. STATISTICAL ANALYSES

Note that standard data derivation rules and stat methods are described in “business rules document” and will not be repeated below.

5.1. Demography

5.1.1. Analysis of demographics/baseline characteristics planned in the protocol

A study flow table will be generated to present the number of subjects screened, randomized, receiving the Fx dose and included in the PPS for analyses of immunogenicity and efficacy.

The analysis of demographics will be performed on the ITTS and on the PPS for analysis of immunogenicity and efficacy.

Demographic characteristics (age at booster vaccination in years for the vaccinated groups and at the time of the screening for the infectivity control group, gender, and race) will be summarized by group and overall using descriptive statistics:

- Frequency tables will be generated for categorical variables such as race.
- Mean, median, standard deviation (SD) and range will be provided for continuous data such as age.

Previous study group (i.e., in the MALARIA-092 study) will be tabulated.

Withdrawal status will be summarized by group using descriptive statistics:

- The number of subjects enrolled into the study as well as the number of subjects excluded from PPS for analyses of immunogenicity and efficacy will be tabulated.
- The number of withdrawn subjects will be tabulated according to the reason for withdrawal.

5.2. Exposure

5.2.1. Analysis of exposure planned in the protocol

The number and percentage of subjects with vaccination will be summarized overall and by group for all study groups where a vaccination is part of the study procedure. The analysis of exposure will be performed on the ITTS.

5.3. Efficacy

5.3.1. Analysis of efficacy planned in the protocol

The analysis of efficacy will be performed on the PPS for analysis of immunogenicity and efficacy.

Efficacy will be assessed by comparison of *P. falciparum* parasitemia incidence and time-to-onset of *P. falciparum* parasitemia after sporozoite challenge. The analysis of the primary objective will be based on blood smears results; additional exploratory analyses will be performed based on PCR results (tertiary objectives).

Vaccine efficacy (VE) is defined as $100 * (1 - \text{Relative Risk})$. Relative risk of infection and 95% CI will be calculated.

Fisher's Exact test will be used for the comparison of *P. falciparum* parasitemia incidence after challenge between each one of the study groups (P-Fx and NP-Fx) and the infectivity control group.

Kaplan-Meier analysis will be performed on time-to-onset of *P. falciparum* parasitemia, for comparisons between each one of the study groups (P-Fx and NP-Fx) and the infectivity control group, using the log-rank statistic.

The same methodology will be applied for the evaluation of the study groups (P-Fx vs. NP-Fx) versus each other. If there are sufficient evaluable subjects (at least a 1:2 ratio between vaccinated and control groups) to draw some conclusions, descriptive analyses based on initial group assignment versus control will be performed.

All statistical tests will be two-tailed at 5% significance level.

Risk periods

For the analyses of time-to-onset of parasitemia (Kaplan-Meier and log-rank), time-at-risk will start on first day of challenge. Time-at-risk will be censored on Visit 22 (Day 50; 28 days post-challenge), drop-out date, start date of anti-malarial treatment or date meeting an endpoint, whichever occurs first. Time-at-risk will be calculated as: censor date – challenge date + 1.

For the analysis of proportion affected (relative risk), all subjects included in the PPS for analysis of immunogenicity and efficacy will be considered at risk of infection and no censoring or elimination will be applied for subjects not completing the entire protocol defined post-challenge follow-up (Day 50; 28 days post challenge).

Case definition

The following will be used as case definition of *P. falciparum* infection:

Asexual blood stage *P. falciparum* parasite density > 0 detected by blood slide reading (or PCR for tertiary objectives).

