NP-Fx	20	18-55 years**	x	x		x
InfectivityCtrl	6-24***	18-55 years			x	x

**P-Fx** = Pooled subjects from the MALARIA-092 study vaccinated with RTS,S/AS01 (different doses/formulations) and protected following the first challenge who will receive a Fx booster dose of RTS,S/AS01E

**NP-Fx** = Pooled subjects from the MALARIA-092 study vaccinated with RTS,S/AS01 (different doses/formulations) and not protected following the first challenge who will receive a Fx booster dose of RTS,S/AS01E

**InfectivityCtrl** = Subjects who will not receive any vaccination but will undergo sporozoite challenge

\*The actual number of subjects will be known after screening. A minimum of 20 subjects per group (P-Fx and NP-Fx) is anticipated

\*\*Age at the time of enrollment in the primary study (MALARIA-092)

\*\*\*Up to 24 subjects, or 4-6 per day, depending on the expected number of days of challenge

**Table 2** Study groups and treatment foreseen in the study

Treatment name	Vaccine/Product name	Volume to be administered	Study groups		
			P-Fx	NP-Fx	InfectivityCtrl
RTS,S/AS01 E	RTS,S	0.1 mL	x	x	-
	AS01E		x	x	-

- **Control:** Non-interventional control. For the challenge, this will be the InfectivityCtrl group.
- **Vaccination schedule:** All previously vaccinated and challenged subjects in MALARIA-092 study will receive one Fx dose of RTS,S/AS01E at Visit 1 (Day 1).
- **Treatment allocation:** Non-randomized.
- **Blinding:** Open (refer to [Table 3](#)).

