### Overview of the recruitment plan

On or about the last study visit of the MALARIA-092 study, participants will be asked about their willingness to be contacted to take part in a booster study, which will also be conducted at WRAIR. The investigator and his team will explain the rationale for MALARIA-102 and explain in general terms what the study entails. Only subjects who have completed all vaccinations and the primary challenge will be eligible for screening for the MALARIA-102 study. Such subjects who are interested in continuing on to participation in the MALARIA-102 study will be contacted and scheduled for a screening visit during the approved study recruitment window. Screened subjects who fulfill all inclusion criteria (and none of the exclusion criteria) for the study will be considered eligible to participate in the study.

For the infectivity control group, subjects will be recruited and screened in order to provide approximately 6 control subjects for each malaria challenge day required for the trial (the number of which will depend on the final number of experimental subjects). Up to 24 subjects may eventually be enrolled (defined as undergoing malaria challenge) as infectivity controls.

To be deemed eligible to participate, control subjects must fulfill all inclusion criteria (and none of the exclusion criteria) for the study. For the infectivity control group **only**, in the rare event that malaria-naïve volunteers cannot be recruited, subjects may be enrolled if they have not been diagnosed with malaria (clinical disease or parasitemia) within the last five years (inclusive).

WRAIR has an established process whereby an IRB-approved generic screening protocol is used to screen potential subjects managed by the WRAIR Clinical Trials Center. If subjects from this pre-screened group agree to be infectivity controls in the MALARIA-102 study, the required biochemistry, hematology, HIV, HCV and HBsAg and ECG test results can be rolled over to the study provided they occur within the screening period, at the discretion of the Principal Investigator.

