### 11.4. Determination of sample size

The target enrollment for the MALARIA-092 study was ~130 vaccinated subjects (~26/vaccine group) and up to 30 subjects (or 4-6 per day, depending on the expected number of days of challenge) in the infectivity control group. Approximately 20 subjects in each group were expected to undergo sporozoite challenge (~100 vaccinated subjects overall). Based on past experience, an approximate 20% will refuse to participate in the booster study and there will be an approximate 20% drop-out rate in vaccinees for the booster study. With an assumed vaccine efficacy (VE) of ~68% in the primary study, there will be a minimum of ~20 subjects per group in this MALARIA-102 study. In addition, up to 24 infectivity control subjects will be newly enrolled for this study.

Assuming at least 19/20 controls and 6/20 vaccinees become positive (VE of ~68%), the trial has 99% power to detect statistically significant vaccine efficacy of each of the vaccination groups over the infectivity controls (p-value < 0.05).

The power to detect a statistically significant VE of each of the vaccination groups over the infectivity controls (p-value < 0.05) is presented in the table below:

Controls (N)	Vaccines (N)	Vaccine efficacy (%)	Protected controls (N)	Protected vaccinees (N)	Power* (%)
20	20	89	1	18	100
20	20	78	1	16	100
20	20	68	1	14	99.1
20	20	58	1	12	94.6
20	20	47	1	10	81.8

\*Two independent proportions power analysis - Test statistic: Fisher exact test

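### Fisher's exact test is valid but conservative at these group sizes; a pre-specified Boschloo test would hold the 5% limit, never lose power, and help most if few controls are challenged (minor, optional).

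*SAP*

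**What the plan says.** SAP 5.3.1, repeating Protocol 11.9, sets the test of incidence: "Fisher's Exact test will be used for the comparison of *P. falciparum* parasitemia incidence after challenge", for P-Fx and for NP-Fx against the infectivity controls. The same methodology is applied to P-Fx against NP-Fx. The level is also fixed there: "All statistical tests will be two-tailed at 5% significance level". VE is one minus the relative risk, reported with a 95% CI whose method is not named.

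Protocol 11.4 bases its power on the same test: "Two independent proportions power analysis - Test statistic: Fisher exact test". Its headline reads "Assuming at least 19/20 controls and 6/20 vaccinees become positive (VE of ~68%), the trial has 99% power", and its lowest-efficacy row is "20 20 47 1 10 81.8" (controls, vaccinees, VE, protected controls, protected vaccinees, power).

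On numbers, Protocol section 3, Table 1 says "A minimum of 20 subjects per group (P-Fx and NP-Fx) is anticipated", and for controls "Up to 24 subjects, or 4-6 per day, depending on the expected number of days of challenge", with 6-24 shown in the table. The recruitment plan in Protocol 5.1 speaks of "approximately 6 control subjects for each malaria challenge day required for the trial". So 6, 12, 18 and 24 controls are all foreseen, while the power table uses 20.

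Protocol 11.12 and SAP 6 describe all analyses as descriptive and the inferential ones as not confirmatory.

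**The concern.** Enrolment fixes the group sizes and the number infected is random. The design therefore does not require Fisher's conditioning on the total number of infections. In small groups that conditioning leaves few attainable p-values, so the true error rate falls well below 5% and power is lost.

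Boschloo's test takes the Fisher p-value as its statistic and recalibrates the cut-off so that the maximum error rate over all common infection rates stays within 5%. Its rejection region contains Fisher's, so it cannot have less power.

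The power at stake cannot easily be found elsewhere. Withdrawals are not replaced (Protocol 10.2), fewer than 20 per group may consent (Protocol 5.1), and the number of controls may be small. NP-Fx consists of subjects who failed the first challenge, so its VE could be low, yet NP-Fx against controls is half of the primary objective.

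**Working it through.** **Inputs.** 20 vaccinees per group (Protocol section 3, Table 1). Controls 6, 12, 18 or 24 (Table 1 and the recruitment plan in 5.1) and 20 (Protocol 11.4). Control infection 19/20 = 0.95 (11.4). Two-sided 5% (SAP 5.3.1).

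**Method.** For 20 vaccinees and m controls, every table (x, y) is enumerated, with x and y the numbers infected. Power is the sum of Bin(x; 20, p_v) × Bin(y; m, p_c) over the rejected tables. Size is the maximum of that sum over a common rate p_v = p_c. The Boschloo cut-off is the largest two-sided Fisher p-value whose rejection region has size at or below 5%. VE = 1 − p_v/p_c, so p_v = 0.50 gives 1 − 0.50/0.95 = 47%, 0.60 gives 37% and 0.70 gives 26%.

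**The plan's own table (20 v 20, control infection 0.95).**

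| VE | Protocol 11.4 | Fisher, 0.05 | Fisher, 0.025 |
|---|---|---|---|
| 68% | 99.1% | 99.7% | 99.1% |
| 58% | 94.6% | 97.4% | 94.6% |
| 47% | 81.8% | 89.4% | 81.8% |

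The headline 99% is reproduced to within a point. The three rows below 100% match two-sided 0.025 to the decimal, not the p < 0.05 stated with the table.

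**Maximum size, and power at VE 47%, control infection 0.95.** Boschloo here uses the two-sided Fisher p-value as its statistic.

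| Controls | Size, Fisher | Size, Boschloo | Power, Fisher | Power, Boschloo | Gain (points) |
|---|---|---|---|---|---|
| 6 | 1.9% | 4.3% | 30.8% | 56.4% | 25.6 |
| 12 | 3.2% | 4.9% | 79.0% | 82.8% | 3.7 |
| 18 | 3.5% | 4.7% | 90.6% | 92.8% | 2.2 |
| 20 | 2.5% | 4.6% | 89.4% | 94.0% | 4.6 |
| 24 | 3.4% | 4.9% | 92.7% | 94.9% | 2.1 |

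Gains are taken before rounding. Over every count from 6 to 24, Fisher's maximum size runs from 1.9% to 4.0% (the latter at 15 and 17 controls). The gain is uneven between counts: at VE 47% it is 0.0 with 17 or 19 controls.

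**Other efficacies.**
- 6 controls: VE 68%, 80.0% to 88.0%; VE 58%, 58.5% to 75.3%.
- 20 controls: VE 68%, 99.7% to 99.8%; VE 58%, 97.4% to 98.8% by rounded values; VE 37%, 71.6% to 80.6%; VE 26%, 44.6% to 54.4%. The last two lie below the plan's table.

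**Version of the test.** Two one-sided Boschloo tests at 2.5% each are also exact. With 6 controls at VE 47% they give 44.6%, a gain of 44.6 − 30.8 = 13.8 points, against 25.6 for the version in the table.

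**All controls infected.** With 18, 20 or 24 controls the two tests have identical power at vaccinee infection rates from 10% to 70%. With 6 controls and 50% of vaccinees infected, power goes from 41.2% to 74.8%; with 12 controls the gain is 3.7 points.

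**P-Fx against NP-Fx.** At 20 v 20, with assumed infection of 10% and 40%, power rises from 49% to 61%. The figures in Protocol 11.4 suggest a larger P-Fx group: 100 × 0.8 × 0.8 × 0.68 ≈ 44, against 100 × 0.8 × 0.8 × 0.32 ≈ 20 for NP-Fx. At 44 v 20 the gain is only 2-4 points.

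**A single table.** Infection in 14/20 vaccinees against 19/20 controls gives Fisher p = 0.091 but lies inside the 5% Boschloo region.

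**The case against.** Fisher's test controls the type I error, and the protocol, SAP and power section all agree on it. It also produced the p-values of the earlier challenge study cited in Protocol 1.1. The analyses are declared non-confirmatory, no success rule depends on p < 0.05, and VE is reported with a CI. All of this stands, and it is why the point is one of efficiency.

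A reader might infer from the figures that the trial gives up 26 points of power. The documents do not support that as a general statement. It needs 6 controls, VE 47% and one version of Boschloo's test. At 20 v 20, on which the plan is powered, Fisher's power is already at least 89% over the tabulated VE range. The earlier study's controls were all infected; if that recurs with 18, 20 or 24 controls, nothing is gained.

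A reader might also take 1.9-3.5% as the error rate to expect. It is the maximum over the common infection rate. At a common rate of 95%, Fisher's error rate is about 0.2-1.3% with 6-24 controls.

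The objection does not remove the point. Six and 12 controls are foreseen outcomes, NP-Fx may have low VE, and interim results will inform a decision on future field trials (Protocol 11.13.1).

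**Conclusion.** The point holds as a minor, optional improvement. Fisher's test is not wrong here. It is conservative, and an exact alternative holds the same 5% limit without ever losing power.

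The size depends mainly on how many controls are challenged. At VE 47% and 95% control infection, the gain is about 14-26 points with 6 controls, about 4 with 12, and 2-5 with 18, 20 or 24. At 20 v 20 it is 0-5 points over the plan's VE range and about 9-10 points at VE 26-37%.

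These figures assume 20 vaccinees per group and independent binomial outcomes. The 95% control infection rate is the plan's own planning value.

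The mismatch in the power table is separate and does not depend on the choice of test. The printed figures understate Fisher's power at the stated level, so the planned sample size is not undermined.

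**What to change.** Before challenge results exist:

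1. In SAP 5.3.1 and Protocol 11.9, name the two-sided Boschloo exact unconditional test, with the two-sided Fisher p-value as its statistic, for P-Fx v control, NP-Fx v control and P-Fx v NP-Fx. The version must be stated because the result depends on it.
2. Keep Fisher's p-value as supportive, for comparability with the earlier challenge study.
3. State that the relative-risk CI is a separate method and may not agree exactly with the p-value.
4. Restate the Protocol 11.4 power table for the chosen test at two-sided 0.05. If Fisher's test is kept, correct the last three rows to 99.7, 97.4 and 89.4%, or state that 0.025 was used.

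The cost is a few sentences in each document and a short validated program, with no extra subject, visit or assay. The downsides are that the main p-value no longer comes from the test used in the earlier study, and that the gain is small if 18 or more controls are challenged. Choosing the test after results are known would look data-driven.
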